5.1.3 Concomitant medications

Only those medications that the patient is taking at baseline on a routine basis or medications that cause an AE will be captured in C3D. {Thus onetime medications, PRN medications, and medications given to treat adverse events will not be captured in C3D.}

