Title: A Phase II Trial of Valproic Acid in Patients with Advanced Thyroid Cancers of Follicular Origin

Principal Investigator: [name].
EOB/CCR/NCI
[name]
[name]
[name]
[contact]
[contact]

Associate Investigators: [name]., EOB/CCR/NCI
[name]., DEOB/CES/NIDDK
[name], R.N., DEOB/CES/NIDDK

[name]., NMD/CC/NIH
[name]., BDMS/OCD/CCR/NCI
[name]., DEOB/CES/NIDDK
[name], PHARM/CC/NIH
[name]., EOB/CCR/NCI
[name]., EOB/CCR/NCI

[name]., EOB/CCR/NCI
[name], R.N.,
OCD/CCR/NCI

[name]., EOB/CCR/NCI

Referral Contacts:

[name], R.N., OCD/CCR/NCI

PRECIS

Background:

- Patients who have advanced differentiated thyroid cancers (Stage IV) have a five-year survival of only 25%. Clinically this results in more aggressive growth, metastasis, decreased or loss of iodine uptake in the tumor, and tumors that may be refractory to conventional treatment: surgical resection, radioactive iodine treatment and thyroid hormone for TSH suppression.
- In thyroid cancer, valproic acid, at clinically achievable concentrations, has an antiproliferative and differentiating effect.
- We hypothesize that valproic acid may inhibit proliferation and induce differentiation in thyroid cancer cells so that ^{131}I may detect residual disease and be more effective for radioiodine ablation of thyroid cancer cells of follicular cell origin.

Objectives:

- The primary goal of this study is to determine if valproic acid will have an antineoplastic and differentiation effect in patients with advanced and or metastatic thyroid cancer of follicular cell origin.

Eligibility:

- Unresectable advanced and or poorly differentiated thyroid cancers of follicular cell origin (excluding anaplastic and medullary thyroid cancer) that have no uptake (<1%) on radioiodine scan or are unresponsive to radioiodine therapy.
- Elevated serum thyroglobulin (Tg) level (>100ng/ml on thyroid hormone; >10ng/ml off thyroid hormone).

Design:

- This will be an open label phase II study to assess the efficacy of valproic acid therapy as an antiproliferative and differentiation agent in patients with incurable differentiated thyroid cancer (unresponsive and/or radioiodine negative and unresectable).
- Oral valproic acid will be administered to reach a therapeutic serum level (50 to 100 $\mu\text{g}/\text{ml}$).

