3 STUDY IMPLEMENTATION

3.1 STUDY DESIGN

Current conventional therapy for patients with thyroid cancers of follicular cell origin after thyroidectomy and ablative treatment with 131-I involves only thyroid hormone for TSH suppression. In this study, patients will receive TSH suppression therapy with valproic acid for 16 weeks.

The total study period will be 18 weeks, with a one year follow up. Patients who respond to treatment as evidenced by decreased Tg level, RAI uptake or decreased tumor size will continue treatment of valproic acid for 1 year.

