3.4 THYROGEN RAI SCAN

All patients will undergo a Thyrogen® (thyrotropin alfa for injection) RAI scan at entry to the study and after completion of 10 weeks of valproic acid treatment. Depending on the results of the scan, patients will continue valproic acid and prepare for an ablation, or will continue with valproic acid.

Procedure:

- Low iodine diet for 2 weeks
- Thyrogen 0.9mg intramuscularly (in the buttocks) every 24 hours x 2 doses
- 123-I radioiodine 24 hours following the last dose of Thyrogen
- Serum Tg and TSH **immediately** prior to the scan
- Scan 48 hours after radioiodine administration (72 hours after thyrogen administration)

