 - CBC with differential, platelets, BUN, creatinine, total protein, total bilirubin, ALT, AST, ALKP, amylase, ammonia, albumin and b-HCG (if applicable).
 - Toxicity assessment and review of diary
- Week 16:
 - Physical exam including ECOG status
 - CBC with differential, platelets, BUN, creatinine, total protein, total bilirubin, ALT, AST, ALKP, amylase, ammonia, albumin and b-HCG (if applicable).
 - Tg, TSH
 - Toxicity assessment and review of diary
 - Ultrasound of the neck and mediastinum
 - MRI or CT of the neck and chest
 - FDG-PET scan
 - Health Related Quality of Life HRQOL) form completion
- Weeks 17-52
 - Patients who show a response by RECIST criteria or have a decreased thyroglobulin level from Day 1 of the treatment (registered as a partial response to the treatment) will continue on valproic acid at their current dose for a total of 52 weeks.

- Stop valproic acid if no response
- Sixteen weeks or 4 months is significant amount of time to measure response to treatment and therefore, if there is a response, a patient's thyroglobulin levels should have decreased by then, as well as, by RECIST criteria.
- Patients who show no response, patients will stop valproic acid treatment and continue with routine follow up.

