5.2 RESPONSE CRITERIA

RAI uptake and Tg level will be compared pre- and post-valproic acid treatment. The nuclear medicine radiologists using a planar technique will measure the RAI scan uptake. The post-valproic acid scan will then be compared side-to-side with the pre-valproic acid scan, using the planar technique, and will then be scored as "increased" or "unchanged" compared to zero/minimal (<1%) uptake seen on the pre-valproic acid scan. We will define 4 categories of response:

1. Complete response: increased RAI uptake on post-valproic acid therapy at week 10, AND a decrease in Tg level to less than 2 ng/ml (or a decrease in Tg-Ab level to less than 2.0 IU/ml) at 10 weeks AND disappearance of all lesions at 16 weeks.
2. Partial response: increased RAI uptake on post-valproic acid scan at week 10, OR a decreased Tg level (or a decrease in Tg-Ab level by more than 20%) at 10 weeks AND 30% decrease in target lesion at 16 weeks.
3. Stable disease: no change in RAI uptake AND Tg levels (or Tg-Ab level) AND no significant change of lesions 16 weeks.
4. Progressive disease: tumor mass increases OR Tg levels (or Tg-Ab levels) increases over 10 weeks OR at least 20% increase in target lesion at 16 weeks.

Target lesions will be evaluated according to the RECIST response criteria outlined below.

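### A thyroglobulin fall counts towards response with no like-for-like rule or TSH condition, 3.5.2 conflicts with 5.2 on whether it suffices alone, and 5.1.3 leaves gaps in recording what else could have caused it

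*Protocol*

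**What the plan says.** **Tg and thyroid hormone.** The precis makes the Tg threshold depend on hormone status: "Elevated serum thyroglobulin (Tg) level (>100ng/ml on thyroid hormone; >10ng/ml off thyroid hormone". Section 3.1 sets the background treatment: "In this study, patients will receive TSH suppression therapy with valproic acid for 16 weeks". No section gives a TSH target or asks for a stable levothyroxine dose before baseline or during weeks 1 to 10.

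**Which Tg is drawn when.** Section 2.2 lists routine TSH and Tg at entry and, as a separate item, a Thyrogen scan with a stimulated Tg. Section 3.4 uses the same preparation at entry and after 10 weeks ("Thyrogen 0.9mg intramuscularly (in the buttocks) every 24 hours x 2 doses"), with Tg and TSH taken just before the scan. Section 3.3 lists Tg and TSH at week 10 beside the scan. Schedule 2 in section 3.5.2 lists Tg and TSH at week 16 without Thyrogen.

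**Response.** In section 5.2 the first element of a partial response is a rise in radioiodine uptake on the week-10 scan. The definition then goes on: "OR a decreased Tg level (or a decrease in Tg-Ab level by more than 20%) at 10 weeks AND 30% decrease in target lesion". The lesion change is judged at week 16. In section 3.5.2, Schedule 2 patients continue valproic acid if they respond by RECIST or "have a decreased thyroglobulin level from Day 1 of the treatment (registered as a partial response to the treatment"). Section 6.2 bases the efficacy count on complete and partial responses as defined in 5.2.

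**Data capture.** Section 5.1.3 says of the trial database (C3D): "Only those medications that the patient is taking at baseline on a routine basis or medications that cause an AE will be captured". It adds: "Thus onetime medications, PRN medications, and medications given to treat adverse events will not be captured in C3D".

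**The concern.** Tg is a response component that, on the protocol's own showing, moves with thyroid hormone status. With no control arm, there are two ways to keep such movement from being read as a drug effect: compare measurements taken under the same condition, or record what changed and allow for it. The protocol requires neither. A Tg fall of any size qualifies, whatever the TSH drawn with it, and the baseline comparator is not named.

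At stake is the efficacy decision, which turns on 3 responses among 20 evaluable patients. One or two misattributed responses could change it. The missing comparator and the limits on drug capture also make a doubtful response hard to adjudicate afterwards.

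**Working it through.** **1. Is the Tg comparison defined?** Entry yields two Tg values, routine and stimulated. Week 10 has a stimulated value from the scan, and the separate Tg line in 3.3 may or may not be a second draw. Schedule 2 week 16 is listed without stimulation. Section 5.2 names no comparator. Section 3.5.2 names Day 1, but no Tg is scheduled that day; the nearest are the entry draws within 2 weeks before treatment. A stimulated entry value could therefore be set against an unstimulated week-16 value. The 20% threshold in 5.2 is attached to Tg antibody, so Tg itself has no minimum fall.

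**2. Can a Tg fall alone be a partial response?**

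| Source | Tg fall alone is a partial response? | What a Tg fall can do |
|---|---|---|
| 5.2 read as (uptake OR Tg fall) AND 30% shrinkage | No | Complete a response in a patient who has the shrinkage but no uptake increase |
| 5.2 read as uptake OR (Tg fall AND 30% shrinkage) | No | The same |
| 3.5.2, Schedule 2 | Yes | Suffice alone |

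Sections 5.2 and 3.5.2 conflict. Section 6.2 points to 5.2, but 3.5.2 says how the patient is recorded.

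**3. What does 5.1.3 leave out?**
- Levothyroxine taken routinely at baseline falls inside the rule. Later dose changes are not mentioned either way.
- A drug first started on study that causes no adverse event is outside the rule. This includes another anticancer drug, which could affect lesion size as well as Tg and so satisfy 5.2 under either reading.
- Starting another anticancer treatment is not among the listed removal criteria in 3.9.1, so such a patient may stay in the response count.

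**4. The stated design, reproduced.** Inputs from 6.2: 13 patients in stage 1, stop at 0 responses; 20 in total, efficacious at 3 or more; null rate 5%. With X1 binomial(13, p) and X2 binomial(7, p):

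P(declare) = P(X1 + X2 ≥ 3) − P(X1 = 0) × P(X2 ≥ 3)

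At p = 0.05: 0.07548 − 0.5133 × 0.00376 = 0.0736, against the stated 7.4%. Early stopping is 0.95^13 = 0.513, against the stated 51%. At p = 0.25 the power is 0.903, against the stated 90%. The sample size needs no correction.

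**5. Sensitivity, only if Tg alone can count.** Let q be the share of true non-responders recorded as responders because something other than valproic acid, or a mismatched test condition, lowered Tg. The documents give no value for q, so these are assumptions. Apparent rate = 1 − 0.95 × (1 − q). Expected false responders = 20 × 0.95 × q if all 20 patients are treated.

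| q (assumed) | Apparent rate | False responders in 20 | Early stop | P(declare efficacy) |
|---|---|---|---|---|
| 0 | 0.0500 | 0 | 0.513 | 0.0736 |
| 2% | 1 − 0.95 × 0.98 = 0.0690 | 0.38 | 0.395 | 0.1525 |
| 5% | 1 − 0.95 × 0.95 = 0.0975 | 0.95 | 0.264 | 0.3025 |
| 10% | 1 − 0.95 × 0.90 = 0.1450 | 1.90 | 0.131 | 0.5616 |

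**The case against.** **Tg alone does not drive the efficacy count.** Section 6.2 refers to 5.2, and both bracketings of 5.2 require more than a Tg fall. The Tg-only route sits in a rule about continuing treatment. This stands, and it means the table in step 5 does not apply if 5.2 is followed strictly. It does not remove the conflict: 3.5.2 states in terms that such a patient is recorded as a partial response.

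**A standardised Tg exists.** Thyrogen is given identically at entry and week 10, so a stimulated-to-stimulated comparison is available and lessens the influence of background TSH. This stands for week 10 if that is the comparison made. The protocol does not say so, and the unstimulated week-16 value remains exposed.

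**TSH is drawn with Tg at entry, week 10 and week 16.** A shift in suppression could be seen in an unstimulated draw. But the response rule does not use it, and a TSH taken after Thyrogen would not show background suppression.

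**Iodine load is partly checked.** Urinary iodine is measured at entry and week 10, and a low-iodine diet precedes the scans. This stands; the iodine item is the lesser part of the capture gap.

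**Stronger readings the text does not support.** A reader might infer that 5.1.3 bars thyroid hormone changes from the database. It does not: it covers baseline routine drugs and is silent on their dose changes, and the named exclusions are one-time, as-needed and adverse-event-treatment drugs. A reader might also infer that primary physicians will adjust levothyroxine at the week 4 or week 8 visits. Those visits list no TSH or Tg, so the protocol supplies no prompt for it.

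**The analysis plan could settle this.** It could clarify the comparator, but the response definition and data capture are fixed here, and no analysis plan recovers data that were not collected.

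**Conclusion.** The point holds in a limited form. Section 5.2 uses a Tg fall as a response component without a minimum size, a stated test condition or a TSH-comparability rule. Section 3.5.2 contradicts 5.2 by letting a Tg fall alone be recorded as a partial response. Section 5.1.3 does not capture new drugs that cause no adverse event and leaves thyroid hormone dose changes unaddressed. A background or test-condition effect **could** therefore be credited to valproic acid; the documents do not show that it will be.

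The 15%, 30% and 56% figures should not be read as the trial's actual type I error. They rest on assumed misclassification shares of 2%, 5% and 10% and on Tg being allowed to count alone. Under 5.2 as written, the exposure is narrower: patients with 30% shrinkage in whom the Tg fall completes the response, and patients given another anticancer treatment that never reaches the database. The matter should be corrected, but it does not invalidate the design.

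**What to change.** - **Section 5.2.** Name the Tg comparison and keep it like for like: stimulated with stimulated, or on suppression with on suppression, against a named entry draw. For unstimulated Tg, count a fall towards response only if the TSH drawn with it lies in the same pre-stated range as at baseline. State the minimum Tg fall that qualifies.
- **Section 5.1.3.** Capture in C3D, with dates and dose, any on-study change of thyroid hormone, any new anticancer treatment, and any iodine-containing drug or contrast. State that Tg falls or lesion shrinkage following another anticancer treatment are not credited to valproic acid.
- **Section 3.5.2.** Reconcile the wording on recording a partial response with 5.2, so that only the 5.2 definition feeds the efficacy count in 6.2. This concerns how response is counted; who continues treatment is for the sponsor and investigators to settle.

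The cost is a few database fields and a few sentences. TSH is already drawn, so no new test is needed, and neither the sample size nor the decision rule changes. The downside is that some Tg falls will no longer be credited.

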5.2 RESPONSE CRITERIA

RAI uptake and Tg level will be compared pre- and post-valproic acid treatment. The nuclear medicine radiologists using a planar technique will measure the RAI scan uptake. The post-valproic acid scan will then be compared side-to-side with the pre-valproic acid scan, using the planar technique, and will then be scored as "increased" or "unchanged" compared to zero/minimal (<1%) uptake seen on the pre-valproic acid scan. We will define 4 categories of response:

1. Complete response: increased RAI uptake on post-valproic acid therapy at week 10, AND a decrease in Tg level to less than 2 ng/ml (or a decrease in Tg-Ab level to less than 2.0 IU/ml) at 10 weeks AND disappearance of all lesions at 16 weeks.
2. Partial response: increased RAI uptake on post-valproic acid scan at week 10, OR a decreased Tg level (or a decrease in Tg-Ab level by more than 20%) at 10 weeks AND 30% decrease in target lesion at 16 weeks.
3. Stable disease: no change in RAI uptake AND Tg levels (or Tg-Ab level) AND no significant change of lesions 16 weeks.
4. Progressive disease: tumor mass increases OR Tg levels (or Tg-Ab levels) increases over 10 weeks OR at least 20% increase in target lesion at 16 weeks.

Target lesions will be evaluated according to the RECIST response criteria outlined below.

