3.5 PHASE 2 WEEKS 11-16

3.5.1 Schedule 1 - Patients who exhibit an increased radioiodine uptake on Thyrogen scan post valproic acid therapy at week 10.

- Week 11:
 - Discontinue Levothyroxine
 - Begin Cytomel for 4 weeks (25 micrograms twice a day)
 - Continue valproic acid for a total of 16 weeks

Note: medication will be dispensed following review of Thyrogen scan
- Week 12 - may be performed by their primary physicians
 - Physical exam including ECOG status
 - CBC with differential, platelets, BUN, creatinine, total protein, total bilirubin, ALT, AST, ALKP, amylase, ammonia, albumin and b-HCG (if applicable).
 - Toxicity assessment, pill count, and review of diary
- Week 14: may be performed by their primary physicians
 - Physical exam including ECOG status
 - CBC with differential, platelets, BUN, creatinine, total protein, total bilirubin, ALT, AST, ALKP, amylase, ammonia, albumin and b-HCG (if applicable).
 - Toxicity assessment, pill count, and review of diary
 - Stop Taking Cytomel.
 - Begin low iodine diet.
- Week 16:
 - Measure TSH, Tg and 24 hour urinary iodine.
 - I-131 Ablative treatment {refer to Section 3.6}.
 - Physical exam including ECOG status
 - CBC with differential, platelets, BUN, creatinine, total protein, total bilirubin, ALT, AST, ALKP, amylase, ammonia, albumin and b-HCG (if applicable).
 - Toxicity assessment, pill count, and review of diary
- Week 17:
 - Post ablation RAI scan {5 days (+/- 2 days) following administration of 131-I}.
 - Ultrasound of the neck
 - MRI or CT of the neck and chest
 - FDG-PET scan
 - Resume Levothyroxine (pre study dose) .

- Stop valproic acid end of week 17
- Toxicity assessment, pill count, and review of diary
- Health Related Quality of Life HRQOL) form completion

3.5.2 Schedule 2 – patients who do not exhibit an increased radioiodine uptake on Thyrogen scan post valproic acid therapy at week 10

- Week 11:
 - Maintain valproic acid dose
- **Note:** medication will be dispensed following review of the Thyrogen scan.
- Week 12:
 - Physical exam including ECOG status
 - CBC with differential, platelets, BUN, creatinine, total protein, total bilirubin, ALT, AST, ALKP, amylase, ammonia, albumin and b-HCG (if applicable).
 - Serum valproic acid levels.
 - Toxicity assessment and review of diary
- Week 14: may be performed by local physician
 - Physical exam including ECOG status

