5.4 SAMPLE STORAGE, TRACKING, AND DISPOSITION

Tumor tissue biopsy samples

Patients who have locoregional or metastatic disease that is amenable to ultrasound guided and or CT scan guided needle biopsy will have this done of the target lesion. This will be performed at study entry and at 10 weeks.

Immediate cytopathologic review will be performed to confirm the presence of tumor cells. The samples will then be stored in -80°C until the immunohistochemistry studies and genome-wide gene expression analysis.

The Na/I symporter expression level will be determined by quantitative RT PCR and immunohistochemistry (11-14). Gene expression levels (differentiation *markers*, *cell cycle and apoptosis regulatory genes*) changes with valproic acid treatment will be determine by using pathway specific gene expression arrays (12,13).

Blood samples

The laboratory studies will be blinded to the response of patients to therapy.

Samples will be sent to the Endocrine Oncology Laboratory for processing:

NCI Endocrine Oncology Branch Laboratory
[name]
[name]
[name]
[contact]

At the completion of the protocol, the investigator will dispose of all specimens in accordance with the environmental protection laws, regulations and guidelines of the Federal Government

and the State of Maryland. Any unintentional loss or destruction of the tissue will be reported to the IRB.

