6.2 SAMPLE SIZE AND POWER ANALYSIS

This is a phase II study aimed at measuring the impact of valproic acid on iodine uptake and on tumor response. Response will be defined as complete or partial response as outlined in section 5.2. The study uses a two-stage Simon optimal design with an interim analysis planned when 13 patients are evaluable for response. If no complete/partial responses are seen at that time the study will close to accrual. The study will proceed to stage II if at least one response is seen among the first 13 patients. At the end of study, if the cumulative number of responses among the 20 evaluable patients is 3 or more, valproic acid will be considered efficacious, while this will not be the case if 1-2 responses are noted. Under the null hypothesis of a true response rate that does not exceed 5% ($p_0=0.05$), the two-stage design will control type I error (α) to be no more than 7.4%, and when the true response rate is at least 25% ($p_1=0.25$), the study has at least 90% power ($\beta=0.10$). The probability of triggering early stopping is at least 51% if the true response rate is 5% or less, and less than 2.5% if the true response rate is 25% or more. If the accrual is stopped at the first stage due to futility, the upper bound of a 95% confidence interval for the response rate will be less than 25%. We will plan to enroll up to 25 patients with the expectation that 20 patients (80%) will be evaluable for response.

The stopping rule for Grade 3 toxicity is set at 15% as the acceptable toxicity rate because the study is designed to detect a treatment efficacy rate of 15% or higher. Therefore, if the acceptable toxicity rate is higher than the expected efficacy rate the study will be stopped.

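### The radioiodine scan that feeds the response endpoint is read in known time order with no numeric cut-off for 'increased', so reading error could inflate the 7.4% false-positive risk

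*Protocol*

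**What the plan says.** Section 5.2 of the protocol has nuclear medicine radiologists measure uptake by a planar technique. It continues: "The post-valproic acid scan will then be compared side-to-side with the pre-valproic acid scan, using the planar technique". The post-treatment scan is then scored on two levels, 'increased' or 'unchanged', against a baseline of zero or minimal uptake (below 1%). No size of change is given that counts as 'increased'.

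The score is used in three places.

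- **Response categories (section 5.2).** Increased uptake is required for a complete response. In the partial response line it comes first, followed by an OR (a fall in Tg or Tg-Ab) and then an AND (a 30% decrease in the target lesion), without brackets.
- **Primary test (section 6.2).** Response means complete or partial response under section 5.2. There is "an interim analysis planned when 13 patients are evaluable for response". The trial stops if none of the 13 responds, and 3 or more responses among 20 count as efficacy.
- **Treatment path (section 3.5.1).** Schedule 1 is for "Patients who exhibit an increased radioiodine uptake on Thyrogen scan post valproic acid therapy at week 10".

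Section 1.3 describes the trial as open label, with valproic acid given to all patients. The only blinding statement in the protocol is in section 5.4: "The laboratory studies will be blinded to the response of patients to therapy".

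**The concern.** Scoring a post-treatment scan as 'increased' against a pre-treatment scan requires the reader to know which is which. The protocol does not say this in words, but the procedure cannot be carried out otherwise. In an open-label trial the reader also knows that the patient has been treated. With baseline uptake close to zero and no threshold, deciding whether faint uptake is new is left to judgement. This is the setting in which expectation can influence a reading.

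The stake is the primary conclusion. The design tolerates a 5% response rate under the null and declares success at 3 of 20, so one or two over-read scans can decide the outcome. The stated error rates hold only if responses are classified without error. Objective 1.1.2, whether valproic acid increases radioiodine uptake, depends on this read however the partial response line is parsed.

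**Working it through.** **Inputs from section 6.2.** Null: "Under the null hypothesis of a true response rate that does not exceed 5" per cent. Alternative: "when the true response rate is at least 25" per cent. Type I error: "to be no more than 7.4" per cent. Power: "the study has at least 90% power". Rule: stop at 0 of 13; success at 3 or more of 20.

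**Assumed inputs, not in the protocol.** f is the chance that a true non-responder's week-10 scan is called 'increased'. g is the share of non-responders who would be classed as progressive regardless of the scan.

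**Step 1: reproduce the design.** With response probability p,

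P(success) = P(X1 = 1)·P(X2 ≥ 2) + P(X1 = 2)·P(X2 ≥ 1) + P(X1 ≥ 3),

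where X1 is binomial(13, p) and X2 is binomial(7, p).

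- p = 0.05: 0.3512 × 0.0444 + 0.1109 × 0.3017 + 0.0245 = 0.0736 (stated 7.4%).
- p = 0.25: 0.1029 × 0.5551 + 0.2059 × 0.8665 + 0.6674 = 0.9030 (stated at least 90%).
- Early stopping: 0.95^13 = 0.513 (stated at least 51%) and 0.75^13 = 0.024 (stated less than 2.5%).

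The plan's figures are correct for error-free classification.

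**Step 2: add reading error, with uptake alone sufficient.** This takes the partial response line as uptake OR (Tg fall AND shrinkage). If a progressive classification overrides the scan, a false call creates a responder only among the remaining non-responders:

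apparent rate p* = 0.05 + 0.95 × (1 − g) × f.

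| f | p*, g = 0 | P(success) | p*, g = 0.5 | P(success) | p*, g = 0.75 | P(success) |
|---|---|---|---|---|---|---|
| 0 | 5.00% | 7.4% | 5.00% | 7.4% | 5.00% | 7.4% |
| 2% | 6.90% | 15.3% | 5.95% | 11.0% | 5.48% | 9.1% |
| 5% | 9.75% | 30.3% | 7.38% | 17.6% | 6.19% | 12.0% |
| 10% | 14.50% | 56.2% | 9.75% | 30.3% | 7.38% | 17.6% |

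The g = 0 columns also cover the case in which progression does not override, and they are the upper bound. There, f = 1% already gives 11.0%, and at f = 5% the chance of stopping early falls from 51% to 26%.

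**Step 3: the other parsing.** Under (uptake OR Tg fall) AND 30% shrinkage, a false call changes the outcome only in a patient whose target lesion has shrunk by 30% and whose Tg or Tg-Ab has not fallen enough to qualify. That group should be small at a 5% null, so the effect on the primary test is small. The protocol gives no figure from which to calculate it.

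**Which parsing?** The comma before OR in the partial response line supports uptake alone. So do sections 1.2 and 3.1, which list uptake, Tg and tumor size as alternative signs of response. The text does not settle it.

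**The case against.** **Progression.** Section 5.2 classes a patient as progressive for any increase in tumor mass, any rise in Tg over 10 weeks, or 20% growth of the target lesion. These patients have advanced, inoperable disease, so many non-responders may progress, and an over-read scan would not rescue them if progression takes precedence. This stands. Section 5.2 does not rank the two categories, although the RECIST table in section 5.2.1.3 lets progression override. The 15%, 30% and 56% are therefore upper bounds, not estimates.

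**Parsing.** The primary test is materially affected only if uptake alone suffices. This also stands, and the size is conditional on it.

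**Measured uptake.** Uptake is measured before the scans are compared, and nothing says the score is purely visual. A reader might infer that the measurement plays no part in the score; the text does not support that. What remains is the missing threshold linking measurement to score.

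**No 'decreased' level.** It is tempting to argue that the two-level scale hides reading noise. With baseline below 1%, however, there is little room for a meaningful decrease, so a third level would reveal little.

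**Direction of bias.** A reader might infer that expectation can only push towards 'increased'. The same read leads to thyroid hormone changes and ablation under section 3.5.1, which is a reason for caution in the opposite direction. The usual presumption favours over-reading, but the protocol cannot establish it.

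**Blinding elsewhere.** Masking the laboratory work does not contradict leaving the scan read unmasked. Agreed; it is only a contrast. Nor is this detail awaiting a later plan, because section 5.2 states the reading procedure itself.

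**Conclusion.** The point holds in conditional form. Section 5.2 prescribes an order-known comparison with no numeric definition of 'increased', in an open-label single-arm trial, and that score enters the primary response definition. The 7.4% type I error is computed correctly but assumes error-free classification.

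If uptake alone can make a partial response, assumed false-call rates of 2%, 5% and 10% raise the false-positive risk to at most 15%, 30% and 56%. With half of non-responders progressing and progression taking precedence, it becomes 11%, 18% and 30%. If shrinkage is also required, the primary test is little affected and the weakness falls mainly on objective 1.1.2. The documents do not support the stronger conclusion that reading bias will overwhelm the 5% null: they give no reader error rate and no progressing share, and they leave the parsing open. The change is still worth making, because a less bias-prone read of the same scans costs little.

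**What to change.** In section 5.2:

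1. Define 'increased' as a pre-set change in the measured percent uptake, with the value chosen by the team before any post-treatment scan is read.
2. Have the existing readers measure and score each pair with dates and labels removed and the order randomised.
3. Lock that score before any labelled clinical read of the same pair. If the labelled read came first, the same readers could recall the pair and the masking would be lost.
4. Use the locked masked score for the response endpoint. Leave the read used for scheduling in section 3.5 unchanged.

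The cost is de-identifying about 25 scan pairs and a slightly longer read at week 10. No extra reader, scan or patient is needed.
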